#### 18.2 Completion/Discontinuation of Subjects

A subject may elect to discontinue study drug at any time for safety, medical, or personal reasons. Patients who choose to discontinue study drug prior to disease progression will be followed in the post study treatment follow up period and continue to undergo regularly scheduled disease assessment until documentation of disease progression or start of an alternative anticancer therapy. All subjects who discontinue study drug will be followed for overall survival and all post progression cancer treatments administered will be recorded. Subjects may at any time withdraw consent for further study participation. No further data will be collected on subjects once consent has been withdrawn. All subjects who discontinue study drug are to complete the study discontinuation procedures indicated in the Schedule of Visits and Procedures (Table 4). The investigator will promptly explain to the subject involved that the study drug will be discontinued for that subject and provide appropriate medical treatment and other necessary measures for the subject. A subject who has ceased to return for visits will be followed up by mail, phone, or other means as much as possible to gather information such as the reason for failure to return and the status of treatment compliance, presence or absence of adverse events, and clinical courses of signs and symptoms, and the information will be recorded in the CRF.

Subjects who discontinue early from the study or treatment will be discontinued for 1 of these primary reasons: adverse event(s), lost to follow-up, subject choice, progressive disease, or administrative/other. In addition to the primary reason, the subject may have indicated 1 or more of these reasons as secondary reasons for discontinuation. Study disposition information will be collected on the appropriate CRF. A subject removed from the study for any reason may not be replaced.

#### 19. Confirmation of Medical Care by Another Physician

The investigator will instruct the subject to tell beforehand when the subject is going to receive medical care by another physician. At each visit, the investigator will ask the subject whether the subject has done so since the last visit or is planning to do so in the future. When the subject is going to receive medical care by another physician, the investigator, with the consent of the subject, will inform the other physician that the subject is participating in the clinical study.

#### 20. Statistical methods

Statistical programming and analyses will be performed using R statistical software and/or other statistical software.

## 20.1 Statistical and Analytical Plans

The statistical analyses described in this section will be performed as further outlined in the Statistical Analysis Plan, which will be included in the clinical study report for this protocol.

## 20.2 Analysis Sets

The analysis sets will be defined as follows:

- Full Analysis Set will include all allocated subjects. This will be primary analysis set for the
  efficacy endpoints.
- Per Protocol Analysis Set will include those subjects who were allocated and received at least one dose of the assigned study drug and had no major protocol deviations. The subjects will complete both baseline and at least one post-baseline tumor assessments (week 6).
- Safety Analysis Set will include all subjects who were allocated and received at least one
  dose of the study drug and had at least one post-baseline safety evaluation (week 6). This
  will be the analysis set for all safety evaluations.
- Pharmacodynamic Analysis Set: All the subjects who have received at least one dose of study drug and have evaluable pharmacodynamic data.

#### 20.3 Demographic and other baseline characteristics

Demographic and other baseline characteristics will be summarized and listed. For continuous demographic/baseline variables including age, weight, and vital signs, results will be summarized and presented as n, number of not available data (NA), mean, standard deviation, median, and minimum and maximum values. For categorical variables such as race/ethnicity, the number and percentage of subjects will be used.

#### 20.4 Prior and concomitant medications

Concomitant medications will be assigned an 11-digit code using the World Health Organization Drug Dictionary (WHO DD) drug codes. Concomitant medications will be further coded to the appropriate Anatomical-Therapeutic-Chemical (ATC) code indicating therapeutic classification. Prior and concomitant medications will be summarized and listed by drug and drug class.

#### 20.5 Efficacy Analyses

All efficacy analyses will be based primarily on the Full Analysis Set and secondarily on the Per Protocol Analysis Set.

Page 76 of 88 Date: April 04th, 2016

Data cut-off for the study primary analysis will take place after the last patient enrolled in the study has performed the second tumor assessment (week 12 after the first dose of study drug, given that first evaluation will be performed 6 weeks after the first dose. Subsequent tumor assessments will be performed every 12 weeks until documentation of disease progression or start of another anticancer therapy.

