#### 4.8 Trial planned duration

Start of Recruitment September 2015

End of Recruitment Period March 2017

3rd tumor assessment of the LP (primary analysis): July 2017

Database Lock for Interim Analysis: October 2017

End of Follow up Period: March 2019

FPFV: September 2015

LPLV: September 2018

Clinical Study Report: September 2019

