#### 7.3 Treatment phase

The treatment phase will begin at the time of allocation of the first subject and will consist of the study treatment cycles. The treatment phase will end when the last patient discontinues the study drug. Prior to the completion of the final primary study analysis, an individual subject will remain in the treatment phase until documentation of disease progression.

Subjects who discontinue study drug administration prior to disease progression will continue to be followed in the treatment phase according to the tumor assessment schedule listed in table 3 (performed at week 6 after the first dose of study drug and then, every 12 weeks or sooner if clinically indicated) until documentation of disease progression or start of another anticancer therapy.

Subjects will be allocated in each primary tumor cohort to receive lenvatinib 24 mg by continuous once daily oral administration. Subjects will undergo safety and efficacy assessment as defined in Table 3. Other reasons for discontinuation of study drug different from disease progression include development of unacceptable toxicity, withdrawal of consent or sponsor discontinuation of lenvatinib development.

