#### 18. Completion/Discontinuation of Subjects

## 18.1 Removal of Subjects from Therapy or Assessment

The sponsor reserves the right to discontinue the study for medical reasons or for any other reason at any time. If the study is prematurely terminated or suspended, the sponsor will promptly inform the investigators/institutions and the regulatory authority(ies) of the termination or suspension and the reason(s) for the termination or suspension. The IEC should also be informed promptly and provided with the reason(s) for the termination or suspension by the sponsor or by the investigator/institution, as specified by the applicable regulatory requirement(s).

The investigator may discontinue treating a subject with the study drug or withdraw the subject from the study at any time for safety or administrative reasons. The subject may decide to discontinue study drug or withdraw from the study at any time for any reason. The reason for discontinuation will be documented. If a subject discontinues study treatment, the subject will enter the follow-up period and be required to complete protocol-specified end of treatment visits, procedures, and survival follow-up unless the subject withdraws consent. The investigator should confirm whether a subject is withdrawing from study treatment but agreeing to continue protocol-specified, end of treatment study visits, procedures, and survival follow-up, or whether the subject is withdrawing consent. If a subject withdraws consent, the date will be documented in the source documents.

Subjects who have discontinued study treatment without progression should have disease assessments every 12 weeks from the date of the last assessment until disease progression is documented or another anti-cancer therapy is initiated.

EudraCT no.: 2015-001467-39

Page 74 of 88 Date: April 04th, 2016

All subjects will be followed for survival and all post disease progression cancer treatments administered will be recorded until death, except where a subject withdraws consent or the sponsor chooses to halt survival follow-up following completion of the primary study analysis.

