#### 20.5.1 Analysis of primary efficacy variable

The analysis of ORR will be performed independently for each study cohort when the last patient included in the corresponding cohort of the study will have at least two tumor assessments (12 weeks after the last patient recruited). The primary objective of the study will be based on the independent central radiology review.

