#### 20.6 Sample Size and Accrual

Sample size has been calculated using single stage design. For considering Lenvatinib as an effective treatment, a success rate of ORR of at least 25% is expected. However, a success rate of 10% or less would be considered unacceptable. With 90% power and a 5% level of significance, a total of 55 patients for each cohort are required.

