Calendar and estimated completion dates	Recruitment Start: September 2015 End of Recruitment Period: March 2017 3rd Tumor assessment of LP (Primary Analysis): July 2017 Database Lock for Interim Analysis: October 2017 End of Follow up Period: March 2019 FPFV: September 2015 LPLV: September 2018 Clinical Study Report: September 2019		

2. Tab	ole of contents	
1. Sy	nopsis	3
2. Tal	ble of contents	6
3. Ab	breviations	7
4. Stu	ıdy objectives and variables	8
4.1	Primary objective(s) and primary variable(s)	
4.2	Secondary objective(s) and secondary variables	
	secondary objective(s) and secondary variables	
4.3	Exploratory objective(s) and variables	
The e	exploratory objectives are:	
	pratory variables:	
	idy populations	
	itistical strategy	
6.1		
6.1.1	Primary analysisSummary statistics	
6.1.2	Statistical inference	
6.2	Secondary analysis	
	econdary analysis will be based on the Full Analysis Set and the Safety Ana	
Set		
6.2.1	Summary statistics	11
6.2.2	Statistical inference	12
6.3	Exploratory analysis	12
6.4	Subgroup analysis	12
6.5	Safety analysis	13
6.5.1	Summary statistics	
6.5.2	Statistical inference	
6.6	Demographic and baseline characteristics	
6.7	Concomitant medications	
6.8	Statistical significance level	
6.9	Statistical model assumptions	
6.10	Transformation of expected variables	
6.11	Handling of missing data	
6.12	Description of the softwares to be used for data analysis	
6.13	Interim analysis protocol	
7. Ref	ferences	16

Confidential Version 2.0

GETNE
TALENT Statistical Analysis Plan

Page 7 of 16 Date: June 04, 2020

3. Abbreviations

AE:

Adverse Event

CgA:

Chromogranin A

CR:

Complete Response

DpR:

Deepness of Response

ECG:

Electrocardiogram

eCRF:

electronic Case Report Form

ETS:

Early Tumor Shrinkage

G1:

Grade 1

G2:

Grade 2

GETNE:

Grupo Español de Tumores Neuroendrocrinos

HPMC:

Hydroxypropyl Methylcellulose

NSE:

Neuron Specific Enolase

OOR:

Objective Response Rate

OS:

Overall Survival

PFS:

Progression-Free Survival

PI:

Principal Investigator

PR:

Partial Response

RECIST:

Response Evaluation Criteria In Solid Tumors

SAE:

Serious Adverse Event

WHO:

World Health Organization

4. Study objectives and variables

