6.13 Interim analysis protocol

The interim analysis will be performed when the last patient included in the corresponding cohort of the study will have at least two tumor assessments (12 weeks after the last patient recruited).

Page 16 of 16 Date: June 04, 2020

7. References

- 1. Guidance for Industry: Clinical Trail Endpoints the Approval of Cancer Drugs and Biologics (May 2007).
- 2. R Core Team (2015). R: A language and environment for statistical computing. R Foundation for Statistical Computing, Vienna, Austria. URL (http://www.R-project.org/).

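### The data cut for the primary ORR is described in conflicting ways, and a cut at week 12 truncates best response in late enrollees, so 90% power is not assured

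*Protocol*

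**What the plan says.** The primary endpoint is ORR by RECIST 1.1 on central review. Protocol 12.2 and SAP 4.1 define it as the proportion with a best overall response of CR or PR, and neither sets a time window. Scans fall at weeks 6 and 12 and then every 12 weeks (Protocol 12.2, Table 4), and they continue after the cut.

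The cut itself is described in four ways:

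- **Study level.** Protocol 20.5: "Data cut-off for the study primary analysis will take place after the last patient enrolled in the study has performed the second tumor assessment". Sections 7.4 and 15.2 say the same, and all three give week 12.
- **Cohort level.** Protocol 20.5.1 analyses ORR "when the last patient included in the corresponding cohort of the study will have at least two tumor assessments", again at 12 weeks.
- **Calendar.** Protocol 4.8 lists "3rd tumor assessment of the LP (primary analysis): July 2017", and the SAP synopsis lists "3rd Tumor assessment of LP (Primary Analysis): July 2017". Both then show a database lock for an interim analysis in October 2017.
- **SAP label.** SAP 6.13 takes over the cohort trigger but begins: "The interim analysis will be performed when the last patient included in the corresponding cohort". SAP 4.3 mentions a separate final analysis and assigns to it only the second and third exploratory objectives.

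Protocol 20.6 sizes each cohort at 55 for 90% power at a 5% level. It expects an ORR of at least 25%, and "a success rate of 10% or less would be considered unacceptable". Neither rate is tied to a time point.

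**The concern.** Best overall response accumulates over scans, so the ORR depends on when the data are cut. The documents agree neither on the unit (study or cohort), nor on the scan number (second or third), nor on the status of the analysis (primary or interim). If the cohorts fill at different speeds, the study and cohort triggers give different datasets.

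The cut also gives patients unequal chances to be counted as responders. A response first seen at week 24 counts for a patient who enrolled early and is missed for one who enrolled in the last weeks. The effect on ORR can only be downward. With 10% and 25% as the two reference rates in 55 patients, a small downward shift is enough to take power below the stated 90%.

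The scan calendar adds a smaller ambiguity. For patients who stop drug before progression, Protocol 7.3 gives scans "performed at week 6 after the first dose of study drug and then, every 12 weeks", leaving out the week-12 scan. Section 18.1 schedules them "every 12 weeks from the date of the last assessment". A patient who stops between weeks 6 and 12 would, under 18.1, have the second scan at week 6 + 12 = 18. For such a patient, second assessment and week 12 are not the same event.

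**Working it through.** **1. Reproduce the stated design.** Inputs from Protocol 20.6: unacceptable rate 10%, target rate 25%, 5% level, 90% power, 55 per cohort. Sidedness is not stated. With an exact one-sided binomial test:

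- P(X ≥ 10 | n = 55, p = 0.10) = 0.0444, whereas P(X ≥ 9) = 0.0944, so the success rule is 10 or more responses.
- P(X ≥ 10 | n = 55, p = 0.25) = 0.911.

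Fifty-five is the smallest n that reaches 90% power under this test, so the stated figure reproduces.

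**2. Size of the margin.** Solving P(X ≥ 10 | 55, p) for p:

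- Power is 90% at p = 24.6%, which is a loss of 1.6% of responses.
- Power is 80% at p = 22.0%, a loss of 11.9%.

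**3. Follow-up at a week-12 cut.** Accrual lasts about 18 months (Protocol 7.1 and 10), or 78 weeks, and is assumed even.

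- Under 24 weeks of follow-up: 12/78 = 15.4%, about 8 of 55 per cohort or 17 of 110. These patients have the week-6 and week-12 scans only.
- Under 36 weeks: 24/78 = 30.8%.
- The first enrollees reach about 78 + 12 = 90 weeks and can have eight scans (weeks 6, 12, 24, 36, 48, 60, 72, 84).

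**4. Effect on ORR and power if the 25% means eventual best response.** The documents give no time-to-response data, so the shares below are assumptions. Let L24 and L36 be the shares of eventual responders first seen at weeks 24 and 36.

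- Week-12 cut: loss = L24 × 12/78 + L36 × 24/78.
- Week-24 cut: loss = L36 × 12/78.
- Observed rate = 0.25 × (1 − loss); power = P(X ≥ 10 | 55, observed rate).

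| L24 / L36 | Loss, week-12 cut | Observed ORR | Power, week-12 cut | Power, week-24 cut |
|---|---|---|---|---|
| 0 / 0 | 0 | 25.0% | 91.1% | 91.1% |
| 10% / 5% | 3.1% | 24.2% | 88.9% | 90.6% |
| 20% / 10% | 6.2% | 23.5% | 86.2% | 90.0% |
| 30% / 20% | 10.8% | 22.3% | 81.4% | 88.9% |

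Slower assumed patterns cost more. If 50%, 75%, 90% and 100% of responders are detected by weeks 12, 24, 36 and 48, power is 79.0% at the week-12 cut and 87.1% at the week-24 cut. This calculation gives each patient their own detection probability.

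**5. If the 25% means the rate at the week-12 cut.** There is no loss, and power stays at 91.1%.

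**6. Calendar.** Recruitment ends in March 2017. For a last start between 1 and 31 March 2017, week 12 falls between 24 May and 23 June 2017, and week 24 between 16 August and 15 September 2017. Both precede the October 2017 lock.

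**The case against.** The strongest reply is that the protocol does name its primary analysis. Sections 7.4, 15.2 and 20.5 all put it at week 12, 20.5.1 places the ORR analysis at the same scan count, and SAP 6.13 repeats that trigger under another label. An early cut with a minimum follow-up is a legitimate choice, and because the bias is downward it cannot raise the false-positive rate. Most of this stands. It does not remove the study/cohort difference, the second/third difference, or the SAP's silence on which analysis carries ORR.

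Four stronger readings are tempting, and the documents do not support them:

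- *The stated power is not delivered.* This is not shown. Section 20.6 ties the 25% to no time point, and the loss appears only under assumptions about late responses.
- *July 2017 means a week-18 scan, so calendar and text describe different designs.* July also fits a week-12 scan with some slack, and the third assessment may count the screening scan. What remains is a mismatch of labels.
- *The sponsor could choose between two ORR results.* No passage assigns ORR to the final analysis, and the protocol links it to the week-12 trigger. SAP 6.1.2 plans no inference on ORR, and the interim label brings no stopping rule or alpha spending. The label does not by itself alter power.
- *Making the final analysis primary would cost no time.* The last patient's last visit is planned for September 2018 and the end of follow-up for March 2019, so the read-out could slip by more than a year.

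On scan timing, the text in 7.3 points to the assessment schedule and may only abbreviate it. The conflict with 18.1 is narrower, but it is real for patients who stop drug between weeks 6 and 12.

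**Conclusion.** The point holds as an inconsistency with a conditional cost. The documents do not state one consistent data cut for the primary ORR, and at a week-12 cut about 15% of patients (even accrual over 78 weeks) would contribute only two on-treatment scans to a best-response endpoint with no window. Any first response after week 12 in those patients is missed, which biases ORR down.

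The 90% power is not assured. It holds at 91.1% if the 25% is the rate expected at the week-12 cut. If the 25% is eventual best response, it falls to between 88.9% and 81.4% under the three assumed late-response patterns in the table, and lower if responses come more slowly. Which case applies cannot be settled from the documents. The plan should be changed, but no failure of the design has been demonstrated.

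**What to change.** - Name one primary ORR analysis per cohort. Take the cut when every patient in that cohort has had the week-24 scan or has stopped tumour assessment.
- In Protocol 20.6, tie the 25% to that cut, and state the success rule (10 or more of 55) and its sidedness.
- Keep any week-12 look as a descriptive interim, labelled as such.
- Align Protocol 4.8, 7.4, 15.2, 20.5 and 20.5.1, the SAP synopsis and SAP 6.13 on unit, scan number, week and label, and say whether the screening scan is counted.
- Reconcile the scan timing in Protocol 7.3 and 18.1 with 12.2 and Table 4.

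The cost is wording in both documents and a primary cut up to 12 weeks later. The last week-24 scan would be due by 15 September 2017, before the planned October 2017 lock, and these scans are already scheduled. Under the three assumed patterns, power recovers to between 90.6% and 88.9%, so the slowest of them still falls slightly short of 90%.

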#### 20.5.1 Analysis of primary efficacy variable

The analysis of ORR will be performed independently for each study cohort when the last patient included in the corresponding cohort of the study will have at least two tumor assessments (12 weeks after the last patient recruited). The primary objective of the study will be based on the independent central radiology review.

#### 20.6 Sample Size and Accrual

Sample size has been calculated using single stage design. For considering Lenvatinib as an effective treatment, a success rate of ORR of at least 25% is expected. However, a success rate of 10% or less would be considered unacceptable. With 90% power and a 5% level of significance, a total of 55 patients for each cohort are required.

#### 20.7 Data Analyses Plans

Summary tables (descriptive statistics and/or frequency tables) will be provided for all baseline variables, efficacy variables, and safety variables, as appropriate. Continuous variables will be summarized with descriptive statistics (n, NA, mean, standard deviation, median and minimum and maximum values). Ninety-five (95) percent confidence intervals may also be presented, as appropriate. Frequency counts and percentage of subjects within each category will be provided for categorical data.

Missing data will be ignored.

Secondary endpoints will be summarized with descriptive statistics. Continuous variables will be summarized with n, NA, mean, standard deviation, median and range. Frequency counts and percentage of subjects within each category will be provided for categorical data. Multivariate regression models may be used to study relations between explanatory variables and primary endpoint. Survival analysis will be performed to analyze PFS, Kaplan & Meyer curves will be presented and possible comparisons will be tested using the log-rank test or the Cox proportional hazard model for multivariate analysis.

Patients with lost of follow-up or treatment discontinuation will be included in the final analysis of primary endpoint if they have at least one tumor assessment and considered as censored data for survival endpoints.

Page 77 of 88 Date: April 04th, 2016

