# 11.10 Prohibited Concomitant Therapies and Drugs

Subjects should not receive other anti-tumor therapies while on study. If subjects receive additional anti-tumor therapies such as chemotherapy, palliative radiotherapy, or immunotherapy, this will be judged to represent evidence of disease progression and study drug will be discontinued. These subjects should complete all off treatment assessments and continue to be followed for survival in the Follow-Up Period.

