## 13.2.1 Baseline period procedures

#### Day 0 (Visit 2)

The results of all screening assessments and evaluations must be completed and reviewed by the Principal Investigator prior to the Baseline Visit. Baseline assessments can be performed either on Day -1 or on Cycle 1/Day 1 prior to treatment, although the hematology, clinical chemistry, and pregnancy assessments may be performed within 72 hours prior to the first dose of study drug (Cycle 1/Day 1). Only those subjects who continue to meet all of the inclusion and none of the exclusion criteria are eligible to continue in the study.

Reasonable efforts should be made to conduct all baseline and subsequent evaluations in the same test order at each visit. This is intended to minimize variability in subject response. It is further recommended, whenever possible, that subjects be evaluated at approximately the same time of the day (e.g., morning or afternoon) at each subsequent visit.

At the Baseline Visit, the following evaluations will be conducted:

- · Reconfirm inclusion/exclusion criteria;
- Allocation to cohort A or Cohort B, no randomization needed for this study as all patients included will receive the same study treatment;
- Evaluate ECOG performance status;
- Update medical and surgical history;
- · Obtain vital signs and weight;
- Perform a comprehensive physical examination if the Screening Visit physical examination
  was performed more than 7 days prior to Cycle 1/Day 1 A symptom-directed physical
  examination will be performed on Cycle 1/Day 1 and at any time during the study, as
  clinically indicated;

- Page 49 of 88 Date: April 04th, 2016
- Collect blood samples for biochemistry and hematology analyses (see Table 5 for the tests to be performed). Screening results may be used if collected within 72 hours pre-dose;
- Collect urine sample and perform urinalysis (see Table 5 for the tests to be performed);
- Collect urine sample from all premenopausal and any postmenopausal women who have been amenorrheic for < 12 months for β-hCG pregnancy testing. Screening pregnancy test results may be used if obtained within 72 hours pre-dose;
- Collect blood samples for biomarker analysis;
- Collect most recently archival tumor-biopsy sections or blocks for identification of predictive biomarkers;
- Record all concomitant medication use;
- · Record any AEs or SAEs;

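### The condition in Protocol 20.7 for counting lost or discontinued patients in the primary ORR is ambiguous, and neither document states how an allocated patient with no post-baseline scan counts

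*Protocol*

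**What the plan says.** Protocol 20.2 defines the primary efficacy population: "Full Analysis Set will include all allocated subjects". Protocol 20.5, SAP 5 and SAP 6.1 repeat that efficacy rests primarily on that set. SAP 4.1 defines ORR as CR plus PR over the total of patients, without naming the set.

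Protocol 20.7 adds two statements. Patients lost to follow-up or discontinuing treatment are "included in the final analysis of primary endpoint if they have at least one tumor assessment", and "Missing data will be ignored".

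Protocol 20.1 says that the analyses "will be performed as further outlined in the Statistical Analysis Plan". The SAP does not carry over the tumor-assessment condition. SAP 6.11 plans no imputation and an analysis of whatever data are available. SAP 4.2 Table A has an explicit PFS rule for death before the first assessment. ORR has no counterpart, and no section of either document expressly says how an allocated patient without a post-baseline scan counts.

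**The concern.** The documents imply two answers and never reconcile them. The Full Analysis Set and the SAP 4.1 denominator imply that an unscanned patient stays in as a non-responder. A post-baseline reading of 20.7, together with the missing-data sentences, implies that the patient drops out.

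A patient with no post-baseline scan cannot have a CR or PR, so exclusion takes patients out of the denominator only. With no control arm, nothing offsets the upward shift, and the result is read against the fixed rates of 10% and 25% in Protocol 20.6. SAP 6.1.2 plans no inference, so the percentage itself is the primary result. Two analysts, one following 20.7 on the post-baseline reading and one following SAP 4.1, could report different primary ORRs from the same data.

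**Working it through.** **1. What counts as a tumor assessment.** Usage does not settle it.

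- Protocol 13.2 calls the screening CT/MRI a baseline tumor assessment. The Per Protocol definition in 20.2 says post-baseline when that is meant. Both favor the literal reading, on which a screening scan is enough.
- Protocol 12.3 calls week 6 the first tumor assessment. Protocol 7.4, 15.2 and 20.5 call week 12 the second. Protocol 20.5.1, on the primary analysis itself, equates two assessments with 12 weeks. These favor the post-baseline reading.
- Inclusion criterion 2 requires measurable disease on CT/MRI, so on the literal reading the condition excludes almost nobody. It has a real effect only if read as post-baseline.

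**2. Who is affected.** These are allocated patients with no post-baseline scan:

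- those lost to follow-up before week 6;
- those withdrawing consent before week 6, since Protocol 18.2 says "No further data will be collected on subjects once consent has been withdrawn";
- those dying before week 6;
- those allocated but never dosed, since "Allocation to cohort A or Cohort B" takes place at the baseline visit (Protocol 13.2.1).

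The 20.7 condition does not expressly name early deaths or never-dosed patients. At the least, they fall under the missing-data wording. Two groups are not counted here. Patients who stop drug before progression should still be scanned every 12 weeks (Protocol 12.2). For patients given other anti-tumor therapy on study, Protocol 11.10 says "this will be judged to represent evidence of disease progression". Protocol 18.2 adds that removed patients may not be replaced.

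**3. The plan's own figure.** Inputs from Protocol 20.6 are 10% unacceptable, 25% expected, 5% significance, 90% power and a single stage. The smallest exact one-sided binomial design is n = 55 with success at 10 or more responses (alpha 0.0444, power 0.911). The stated 55 reproduces, so the sample size is not in dispute. The cut-off of 10 is derived here; neither document states one.

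**4. Size of the shift.** The documents give no unassessed fraction q. I assume 0 to 20%, that is 0 to 11 of 55.

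Apparent ORR = all-allocated ORR / (1 − q). For an all-allocated rate of 10%:

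| q | 0% | 5% | 10% | 15% | 20% |
|---|---|---|---|---|---|
| Apparent ORR | 10.0% | 10.5% | 11.1% | 11.8% | 12.5% |

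An all-allocated rate of 22.5% shows as 0.225/0.90 = 25% at q = 10%.

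In whole patients, with r responders and k unassessed, the two answers are r/55 and r/(55 − k):

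| r | All allocated | k | Unassessed excluded |
|---|---|---|---|
| 13 | 13/55 = 23.6% | 3 (5.5%) | 13/52 = 25.0% |
| 12 | 12/55 = 21.8% | 7 (12.7%) | 12/48 = 25.0% |
| 11 | 11/55 = 20.0% | 11 (20%) | 11/44 = 25.0% |
| 6 | 6/55 = 10.9% | 1 (1.8%) | 6/54 = 11.1% |
| 5 | 5/55 = 9.1% | 6 (10.9%) | 5/49 = 10.2% |

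For r = 13, 12 and 11, k is the smallest number that brings the ORR to 25%. For r = 5 it is the smallest that takes it above 10% (5/50 is exactly 10.0%).

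**The case against.** The strongest reply is that the documents already answer the question by implication. The primary set is all allocated patients, and ORR is responders over the total. A patient with no scan has no CR or PR, so stays in the denominator and out of the numerator with no imputation needed. The literal reading of 20.7 is harmless, and the SAP, to which the protocol defers for detail, drops the sentence.

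Much of this stands. It is why the text is called ambiguous rather than contradictory. It does not close the gap. The protocol sentence remains in force, has effect only on the reading that conflicts, and was replaced in the SAP by reliance on available data rather than by a rule.

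A second reply is that 10% and 25% are planning rates, not observed cut-offs. Against the derived rule of 10/55, the examples with 11, 12 and 13 responders already succeed (one-sided p = 0.019, 0.007 and 0.003), and those with 5 and 6 fail either way. That is correct. A design-based conclusion flips only in a narrow case: with 9 responders, 9/55 = 16.4% (p = 0.094) becomes 9/48 = 18.8% (p = 0.046) once seven patients are excluded. Because the SAP plans no test, these p-values show sensitivity only. The point rests on the reported percentage and makes no claim about error rates.

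It is also fair that never-dosed patients should be few, because allocation falls on the day before dosing or on the day itself.

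**Conclusion.** The concern holds and should be fixed. The 20.7 condition has two readings that the documents' own usage cannot separate, and neither document expressly says how an unscanned allocated patient enters the primary ORR. Any resulting error runs in one direction: the ORR is unchanged or too high.

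The size depends on an unassessed fraction that the documents do not give. At the low end the effect is small, 0.2 percentage points with one such patient and 6 responders. At an assumed 20%, a 10% rate shows as 12.5% and 20.0% shows as 25.0%. If every patient has a post-baseline scan, or if 20.7 is read literally and unscanned patients are kept as non-responders, there is no effect.

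**What to change.** - In Protocol 20.7, delete the tumor-assessment condition for the primary endpoint.
- Exempt ORR from the missing-data sentence in 20.7 and from SAP 6.11.
- State in Protocol 20.7 and SAP 4.1/6.11: *The ORR denominator is every allocated patient in the cohort; a patient without an evaluable post-baseline central assessment counts as a non-responder.*
- Report the number of unassessed patients in each cohort.
- If wanted, give the ORR in assessed patients as a labelled sensitivity analysis.

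The cost is wording, with no new data and no change to the sample size. The protocol change has to go through the amendment procedure in Protocol 17.1. The SAP sentence alone would settle the counting rule in practice, but would leave the 20.7 text to be reconciled. The reported ORR may come out slightly lower.
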